Recruitment for this study will draw from families who fled Venezuela and relocated to Colombia within the last year. Included among this population are families originally born in Colombia who had previously emigrated to Venezuela for at least five years and subsequently returned to Colombia. Eligibility requirements include adolescent girls aged 13-19 years old who: live with a male and female caregiver and an adolescent male sibling or relative; immigrated to Colombia within the last year; are available, along with their family members, to participate in the SSAGE intervention for three months; and are available to participate in survey questionnaires immediately before and one month after the intervention (please see Figure 1 for a study schedule). We will recruit 180 adolescent girls from 180 families. Study participants will be recruited by Mercy Corps and consented and enrolled in the study by Los Andes University.

Figure 1. Schedule of enrolment, interventions, and assessments

DATA ANALYSIS AND DISSEMINATION												
Analysis					X	X	X	X	X	X		
Write-up of findings									X	X	X	X
Dissemination											X	X

Subject Recruitment, enrollment, treatment assignment and sample size

Following confirmation of eligibility criteria, the study team will obtain informed parental consent and direct assent from potential adolescent girl participants. Every adolescent girl recruited to the study will be assigned a unique study identification number to enable tracking survey responses across points of data collection.

Sample size and power analysis: To detect a medium effect size in our primary outcomes of interest of $d=0.5$, assuming statistical power of 80% and a one-sided alpha of 0.05, we need a sample size of 63 adolescent girls in each study arm. We expect approximately 20% attrition from baseline to T2 either through: (1) declining to participate in subsequent rounds of data collection or (2) data collectors' inability to locate the participant. Additionally, when estimating the effect of SSAGE on the four outcomes of interest, we will exclude adolescent girls already exhibiting above-threshold scores on the four-dimension measure of mental health symptoms at baseline as it would not be possible to 'prevent' mental health disorders in this subgroup. We expect this to result in the loss of an additional 10% of the initial sample. As such, we require a sample size of 90 girls for each study arm.

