Qualitative implementation evaluation data—including key informant interviews with program staff and mentors (n=8) (43) and semi-structured in-depth interviews with a subset of individuals in the treatment arm (n=24)—will be conducted immediately following the end of the intervention to assess program acceptability, feasibility, and fidelity, and to identify implementation determinants (i.e., barriers and facilitators) that may influence the quality of program delivery.(44,45) Program participants will be purposively sampled in order to ensure representation from all cohorts (male caregivers, female caregivers, adolescent boys, and adolescent girls) as well as levels of adherence to the treatment protocol including number and length of sessions delivered as well as attendance. By also including participants with low attendance, we will be able to explore fidelity as well as potential barriers to acceptance and feasibility. Program mentors and staff will also be purposively sampled to ensure representation across target cohorts and levels of oversight, respectively, in order to inform an exploration of implementation determinants. Interview guides will be guided by the Exploration, Preparation, Implementation, and Sustainment (EPIS) Framework(46,47) and Implementation Outcomes Framework(48) and will focus on the facilitators of and barriers to program implementation as well as the acceptability, feasibility, and fidelity of SSAGE. Interviews will be recorded, translated, transcribed, and cleaned for analysis.

SSAGE's acceptability and feasibility will also be measured through administration of the acceptability and feasibility sub-scales of the Mental Health Implementation Science Tools (mhIST). These two scales will be administered to all treatment participants (n=90) at T2, as part

of the quantitative survey.(49) The mhIST was developed specifically for use in low-resource settings and the tool has been validated in multiple low- and middle-income countries, including in Colombia.(49) Each scale includes 15 questions that are answered by the respondent using a Likert scale.

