5.1. Intent-to-Treat (ITT) Analysis

OLS regression models will estimate the average treatment effect of assignment to the treatment group on changes in each outcome.

Models:

1. Bivariate association between treatment assignment and outcome change.

2. Model 1 + controls for baseline value of outcome.
3. Model 2 + controls for baseline covariates associated with outcome of interest at baseline.

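### SSAGE girls very likely share mentors or groups, but every planned model and the sample size treat girls as independent; if outcomes correlate within mentor or group, standard errors will be too small

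*Protocol*

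**What the plan says.** Girls are randomized individually, 90 per arm, one girl per family (Protocol, Subject Recruitment, enrollment, treatment assignment and sample size). Clustering by family is therefore not an issue.

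Delivery is visible only indirectly, in the protocol's Implementation evaluation section. On whom to interview, it says "Program mentors and staff will also be purposively sampled to ensure representation across target cohorts". Participants are to be sampled across "levels of adherence to the treatment protocol including number and length of sessions delivered as well as attendance". So there are mentors, sessions and attendance records. How girls are allocated to mentors, and whether sessions are held in groups, is not described.

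The analyses are generalized linear regression for the primary outcomes, and linear regression and structural equation modelling for the secondary and mediation analyses (Protocol, Statistical methods). SAP 5.1 says "OLS regression models will estimate the average treatment effect of assignment to the treatment group on changes in each outcome", and SAP 5.2 uses two-stage least squares. None of these mentions a mentor or group effect, or clustered standard errors. The reference list contains texts on hierarchical models, but no such model is specified.

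The sample size targets d = 0.5, "assuming statistical power of 80% and a one-sided alpha of 0.05", and concludes "we need a sample size of 63 adolescent girls in each study arm". This is raised to 90 per arm for losses, with no design effect.

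**The concern.** When treatment is delivered by people, participants treated by the same person, or together, tend to have more similar outcomes than participants treated apart. Here that similarity could arise only in the SSAGE arm, because control girls receive care as usual. The design would then be partially nested: clustered in one arm, independent in the other.

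Ordinary regression ignores that correlation. The treatment estimate itself is not biased by it, but its standard error is too small. Confidence intervals are then too narrow, and the test rejects a true null more often than its nominal level.

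The protocol names effectiveness as its primary objective, plans a hypothesis test and states a power, so the validity of the standard error matters even in a pilot. The protocol itself expects the number and length of sessions to vary and looks for factors affecting the quality of delivery. Such variation is a plausible source of differences between mentors.

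**Working it through.** **Inputs from the protocol.** d = 0.5; 80% power; alpha 0.05, labelled one-sided; 63 analysed per arm. For losses: "We expect approximately 20% attrition from baseline to T2", and a further "loss of an additional 10% of the initial sample" for high baseline scores.

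**Inputs assumed.** The documents give neither the number of analysed girls per mentor or group (m) nor the ICC of the analysed outcome. The main range is m from 6 to 15 and ICC from 0.02 to 0.10, with lower ICCs shown for comparison.

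**The plan's own figure.** Per arm, n = 2(z_alpha + z_beta)² / d².
- Two-sided 0.05: 2(1.960 + 0.842)² / 0.25 = 62.8, so 63. This matches the protocol.
- One-sided 0.05: 2(1.645 + 0.842)² / 0.25 = 49.5, so 50. This does not match.
- Losses: 63 / (1 − 0.20 − 0.10) = 63 / 0.70 = 90. This matches.

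The figure of 63 is thus reproduced only as a two-sided calculation. The mismatch with the one-sided label is a separate matter, but because of it both readings are shown below. No design effect enters at any step.

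**Effect of clustering in one arm.** In SD units with n = 63 per arm:
- Design effect in the SSAGE arm: DE = 1 + (m − 1) × ICC.
- True SE / SE under independence: R = √((DE + 1) / 2).
- True error: two-sided 2[1 − Φ(1.960 / R)]; one-sided 1 − Φ(1.645 / R).
- Power with the correct SE: Φ(0.5 / √((DE + 1) / 63) − z_alpha).

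Worked example, m = 10 and ICC 0.05: DE = 1 + 9 × 0.05 = 1.45; R = √(2.45 / 2) = 1.107; two-sided error = 2[1 − Φ(1.771)] = 7.7%. The correct SE is √(2.45 / 63) = 0.197, so two-sided power = Φ(2.535 − 1.960) = 72%.

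| m | ICC | DE | R | Error, two-sided | Error, one-sided | Power, two-sided | Power, one-sided |
|---|---|---|---|---|---|---|---|
| any | 0 | 1.00 | 1.000 | 5.0% | 5.0% | 80% | 88% |
| 8 | 0.01 | 1.07 | 1.017 | 5.4% | 5.3% | 79% | 87% |
| 6 | 0.02 | 1.10 | 1.025 | 5.6% | 5.4% | 78% | 86% |
| 10 | 0.05 | 1.45 | 1.107 | 7.7% | 6.9% | 72% | 81% |
| 15 | 0.10 | 2.40 | 1.304 | 13.3% | 10.4% | 58% | 69% |

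**Check by simulation.** Forty thousand replicates with 63 per arm, clustering in one arm and an ordinary t-test gave a two-sided error of 7.3% for 7 groups of 9 at ICC 0.05 (formula 7.4%). For 3 groups of 21 at the same ICC, the result was 11.1% (formula 11.0%). The approximation is adequate.

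**The case against.** A reader might infer that the protocol documents shared mentors and group sessions, and that the standard errors are therefore certainly too small. The documents do not support that. The sentence on mentors concerns whom to interview. The cohorts it refers to are participant types (male caregivers, female caregivers, boys, girls), not delivery groups. The figure of 8 in the same section is an interview sample of staff and mentors together, not a count of mentors. Delivery of a whole-family programme family by family would fit the text on sessions and attendance too. Nor is a positive ICC documented; at zero there is no inflation, and at 0.01 with 8 per group it is slight.

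Two further objections concern size. On the protocol's stated one-sided alpha the inflation is smaller. Power under independence is then 88%, so at 10 per group and ICC 0.05 it is still 81%, above the stated 80%. And if the assumed group sizes were enrolled rather than analysed girls, 30% losses would shrink them: 15 becomes 10.5, and the two-sided error at ICC 0.10 falls from 13.3% to 10.7%; 10 becomes 7, and at ICC 0.05 it falls from 7.7% to 6.8%.

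All of this stands as a limit on certainty and size. It does not remove the point. For no two SSAGE girls to share a mentor, the programme would need 90 mentors for the girls alone, and nothing in the documents suggests that. Sharing a mentor can create clustering even if no session is held in a group. An unknown ICC is no reason to set it to zero, which is what the named analyses do.

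**Conclusion.** The point holds conditionally. It is established that no named analysis and no step of the sample size allows for correlation among SSAGE girls, and that the delivery format is not described. It is inferred, though very likely, that girls share mentors or groups. If their outcomes correlate within mentor or group, the planned standard errors will be too small.

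Over the assumed main range, the standard error is understated by a factor of 1.025 to 1.30. The consequence runs from minor at the low end to a two-sided error more than double the nominal level at the high end. The stated 80% power is overstated throughout that range on the two-sided reading, the only one that reproduces 63 per arm. On the one-sided reading it falls short only towards the upper end. These figures illustrate the possible size; they are not estimates for this trial. The plan should be changed because it gives no means of showing that independence holds, and the remedy is cheap.

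**What to change.** 1. State in the protocol and SAP how sessions are delivered and how girls are allocated to mentors, and record a mentor or group ID for each SSAGE girl.
2. Where mentors or groups are shared, use one of two methods in SAP 5.1: a partially nested model (random effect for mentor or group in the SSAGE arm only, small-sample degrees of freedom), or cluster-robust standard errors with each control girl as her own cluster and a correction for few clusters. Use such cluster-robust standard errors in SAP 5.2.
3. Restate power at the planned sample size over a range of ICCs including zero. No additional enrolment is asked for.

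The cost is one ID variable and a few lines of SAP text. The ID may be hard to reconstruct if it is not recorded during delivery. Intervals become somewhat wider and the stated power slightly lower; if the ICC is near zero, the results will be about the same as under the present plan. An estimated ICC would also help in planning a later trial.

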Title: Sibling-Support for Adolescent Girls (SSAGE): A study protocol for a pilot randomized-controlled trial of a whole-family, gender transformative approach to preventing mental illness among forcibly displaced adolescent girls

NCT number: NCT06078124

Date: July 20, 2024

Statistical Analysis Plan (SAP)

Study Title: Sibling-Support for Adolescent Girls (SSAGE): A study protocol for a pilot randomized-controlled trial of a whole-family, gender transformative approach to preventing mental illness among forcibly displaced adolescent girls

Study Type: Pilot Randomized Controlled Trial (RCT)

Version: July 2024

1. Objectives

- To assess the impact of the SSAGE intervention on adolescent girls' anxiety and depressive symptoms, self-esteem, family functioning, gender equitable household task sharing, and coping skills
- To estimate both the intent-to-treat (ITT) and the local average treatment effect (LATE) of the intervention using instrumental variable analysis.
- To explore the role of participant characteristics in loss to follow-up and outcome changes.

2a. Primary Outcomes

- DSM-V cross-cutting youth: Respondents will be asked to indicate the frequency of 19 symptoms in the previous two weeks, selecting from the following response options: 0- Never; 1- Rarely (1 or 2 days); 2- Slightly (between 3 and 6 days); 3- Moderately (more than 7 days of the last two weeks); and 4-Severely (Every day in the last two weeks). Respondents will also report whether they have engaged in each of five behaviors related to drug and alcohol use, self-harm and suicide ideation (answering yes or no) in the last two weeks and whether they have ever attempted suicide in their lifetime (yes or no). The included symptoms are meant to represent 12 domains of mental disorders: somatic symptoms, sleep problems, inattention, depression, anger, irritability, mania, anxiety, psychosis, repetitive thoughts and behaviors, substance use, and suicide ideation/attempts. A respondent will be flagged as requiring further inquiry for a given domain if they answer '2' or higher on at least one of the symptoms in each respective domain. As such, this outcome will be operationalized as 12 dichotomous variables reflecting the 12 domains.
- Depression and anxiety symptomology: Will be measured using the Revised Children's Anxiety and Depression Scale (RCADS-25). The RCADS-25 asks respondents to indicate how frequently they have experienced each of 25 symptoms. Possible responses include 0- Never; 1-Sometimes; 2-Frequently; and 3-Always. An overall RCADS-25 score will be created by adding the responses across all 25 items and looking up the corresponding T-score from a previously created T-score chart based on gender and grade.

2b. Secondary Outcomes

- Family functioning: A modified version of the Family Attachment Changeability Index 8 (FACI-8) will be used to measure family functioning. This version includes 12 items (some are reverse scored) and asks respondents to indicate how common each item is on a 4-point likert scale from “never” to “always.” Scores may assume a value from 12 to 48, with higher scores signaling greater family functioning.
- Self-esteem: captured using the Rosenberg Self-Esteem Scale (RSES). The RSES asks respondents to indicate their level of agreement with ten statements on a 4-point likert scale ranging from “totally disagree” to “totally agree”. After reverse scoring five of the ten items, the final score represents the sum of all items. Scores may assume a value from 10 to 40 where higher values reflect greater self-esteem.
- Coping: A modified version of KidCOPE will be used to assess the use of 15 healthy and unhealth coping strategies in the last two weeks. For each coping strategy, respondents will be able to indicate how often the strategy was employed in the last two weeks using a 4-point likert scale ranging from “never” to “almost all of the time.” Each coping strategy will be examined separately.

3. Study Sample

Eligibility criteria included adolescent girls who had migrated from Venezuela or who were born in Colombia and had previously emigrated to Venezuela for at least five years and recently returned to Colombia. In order to minimize community tensions between migrant and host populations, a few adolescent girls from internally displaced or host families who met all other inclusion criteria were included in the study. Other eligibility criteria included being 13-19 years old, being available to participate, along with their family members, to participate in the SSAGE intervention for twelve weeks, and being available for endline data collection immediately following the completion of SSAGE.

4. Descriptive and Baseline Analysis

- Baseline Balance: Descriptive statistics will be computed separately by study arm. Mean comparisons will be conducted using independent samples t-tests.
- Imbalance Adjustment: Outcomes found to differ significantly at baseline between groups will be included as controls in regression models of change scores.

5. Estimating Treatment Effects

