5.2. Instrumental Variable (IV) Analysis

Participants are considered to have adhered to the intervention if they received both a completion certificate and seed capital.

Two-stage least squares (2SLS) using `ivregress 2sls` in Stata.

Stage 1: Predict adherence using treatment assignment as an instrument.

Stage 2: Estimate the causal effect of adherence on outcome changes.

6. Handling Attrition

- Attrition Analysis: Logistic regression will assess whether loss to follow-up is associated with baseline characteristics.

7. Sensitivity Analyses

Compare results using:

- Change scores vs. endline-only models controlling for baseline values.

8. Software

All analyses will be conducted in Stata (version 16), using appropriate packages for regression, 2SLS, and multiple imputation.

9. Ethical Considerations

All study protocols and procedures were approved by the Washington University in St. Louis IRB (Approval #202407174).

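### SAP 2a flags all 12 DSM-V domains by a '2 or higher' cut, but the substance-use and suicide items are yes/no, so two primary binary variables do not work as written

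*SAP*

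**What the plan says.** SAP section 2a describes three kinds of item in the DSM-V cross-cutting measure:

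- 19 symptoms over the previous two weeks, each rated 0 to 4, where 2 means 3 to 6 days.
- Recent behaviours over the last two weeks: "each of five behaviors related to drug and alcohol use, self-harm and suicide ideation (answering yes or no").
- One further item: "whether they have ever attempted suicide in their lifetime (yes or no").

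It names 12 domains, and the list ends with "repetitive thoughts and behaviors, substance use, and suicide ideation/attempts". One flag rule follows: the answer must be '2' "or higher on at least one of the symptoms in each respective domain". From that rule the SAP concludes that "this outcome will be operationalized as 12 dichotomous variables reflecting the 12 domains".

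These variables then go into the effect models. SAP 5.1 says "OLS regression models will estimate the average treatment effect of assignment to the treatment group on changes in each outcome", and lists three models. The second stage in SAP 5.2 reads: "Estimate the causal effect of adherence on outcome changes". Protocol Table 1 names the instrument and expects a decrease in mental illness, but gives no scoring rule.

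**The concern.** The only stated cut-point does not fit the response format of the items on which two domains appear to rest. A yes/no answer has no value of 2 on the 0-4 scale, and the SAP gives no other route to a flag. The two domains concerned are substance use and suicide.

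The natural repair is to count any 'yes', and that is probably what was meant. It leaves two choices open. Self-harm is asked about but appears in none of the 12 domain names. The lifetime-attempt item looks backward without limit, so it behaves differently from the others in a change score. Both choices decide who is flagged on a primary outcome. The Protocol says randomization is not blinded, so they should be fixed in writing before anyone sees results by arm.

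**Working it through.** **Count the plan's own figures.** The domains listed in SAP 2a number 12, which agrees with the stated 12 variables. The items are 19 graded + 5 recent yes/no + 1 lifetime yes/no = 25.

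**Share outside the rule.** Items: 5 + 1 = 6, and 6/25 = 24%. Domains that by name depend on those items: substance use and suicide ideation/attempts, 2/12 = 16.7%.

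**Apply the rule to a yes/no answer.**

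| Coding of no/yes | Value of 'yes' | Is it 2 or more? |
|---|---|---|
| 0/1 (usual) | 1 | No |
| 1/2 | 2 | Yes |
| Left as yes/no | none | Rule does not apply |

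The SAP states none of these. Only the 1/2 coding lets a 'yes' raise the flag.

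**Try both readings of 'symptoms' in the rule.** If it means only the 19 graded items, the six yes/no items have no stated part in any flag. If it means all 25, a 'yes' coded 1 falls below the cut. Under either reading the two flags could be raised only by a graded item belonging to those domains. The SAP gives no map that shows one, and it describes its drug, alcohol, self-harm and suicide items only as yes/no.

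**Estimates that use the two variables.** SAP 5.1 lists 3 models and SAP 5.2 describes 1, so 2 x (3 + 1) = 8 change-score estimates.

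**Test the 'any yes' repair with the lifetime item included.** Score the flag 1 if raised and 0 if not, with change = endline minus baseline.

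- A girl who truly answers 'yes' to a lifetime attempt at baseline must truly answer 'yes' at endline. Her flag is 1 both times, and her change is 1 - 1 = 0, whatever happens to her recent ideation.
- A girl who answers 'no' at baseline can stay at 'no' or move to 'yes'. On this item her change is 0 or +1, never -1.

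For girls in the first group, the suicide flag therefore cannot show an improvement in either arm. The documents give no prevalence of lifetime attempts, so the size of the resulting dilution is not estimated here.

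**The case against.** The best defence is that this is missing detail and not an error. The SAP calls the graded items symptoms and the recent yes/no items behaviours, and the cut refers to symptoms. A yes/no answer is already binary and needs no cut-point. Table 1 cites a scoring source that cannot be seen here and may supply the rule. A 1/2 coding, or a graded item in either domain, would also let the flag be raised.

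Part of this stands: the failure is conditional on coding and mapping that the SAP leaves unstated. But the same paragraph says that the symptoms represent all 12 domains, and it derives all 12 variables from the one rule. A stated rule that does not fit its items is more than an omission.

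Three stronger readings are tempting, and the documents do not support them.

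- A reader might infer that both variables will certainly be 0 for every girl, and that this would pass as a finding of no effect. The first part assumes 0/1 coding and no graded item in either domain. The second is implausible: an all-zero outcome gives a coefficient of 0, a standard error of 0 and no p-value, which an analyst would notice.
- A reader might say that the lifetime item contradicts the decrease expected in Table 1. That direction is given for mental illness as a construct, and the hypothesis compares arms. Fewer new attempts under SSAGE would be consistent with it.
- A reader might add the check in SAP section 7, "Change scores vs. endline-only models controlling for baseline values", to the count of affected estimates. With the same baseline value in the model, OLS on change and OLS on endline give the same arm coefficient. The check therefore duplicates Model 2.

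One could also object that dropping the lifetime item redefines a domain named for ideation and attempts. That is fair, and it is why the item should be reported separately and the flag relabelled.

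**Conclusion.** The point holds in conditional form. Unless an unstated coding or item map applies, a 'yes' on 6 of the 25 items cannot raise the flag for substance use or for suicide ideation/attempts, and 2 of the 12 primary binary variables do not work as written. The likely intent, any 'yes', still needs two decisions in writing: where self-harm belongs and how the lifetime-attempt item is used. The argument on the lifetime item assumes truthful answers at both surveys and applies only if that item enters the change-scored flag.

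The defect does not invalidate the trial. The RCADS-25 score does not depend on the rule, the other ten domains can be flagged from 0-4 items, and no sample-size figure changes. It should be corrected before the analysis.

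**What to change.** Amend SAP 2a in two places.

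1. Flag substance use and suicide ideation/attempts on any 'yes' to their last-two-weeks items, or on '2' or higher on any graded item placed in that domain. State the domain of each of the five yes/no items, including self-harm.
2. Leave the lifetime-attempt item out of the change-scored suicide flag, and label that flag as covering recent items. Report separately, by arm, the new 'yes' answers at endline among girls who said 'no' at baseline.

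The cost is a few lines. The items are already in the survey, and no new data are needed. There are two downsides. Any 'yes' is a low bar for substance use: one recent drink would flag a girl of 18 or 19. And a new attempt without a 'yes' on a recent item would appear only in the separate report.

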Before each participant leaves the data collection site, their data will be reviewed by a data collector for completion. All data will be incrementally backed up each day on a secure data system and a full back-up will be performed weekly. The research team at Washington University in St. Louis will be responsible for weekly data checks to ensure data quality; errors will be reported to the local field team and rectified. Only selected, authorized WRC, Mercy Corps, University of Los Andes, and Washington University staff will have access to the password-protected data.

Table 1. Primary and secondary outcomes and hypothesized direction of change

Construct as presented in Figure 1	Source of measure	Hypothesized direction of change
Primary outcomes of interest		
Mental illness	DSM-V cross-cutting youth (35)	Decrease
Anxiety and depression	Revised Child Anxiety and Depression Scale-25 (36)	Decrease
Secondary outcomes/mediators		
Gender equitable family functioning	Gendered responsibilities scale (37)	Increase
Family attachment	Family Attachment and Changeability Index (FACI8) (38)	Increase

Improved self-esteem	Rosenberg Self-Esteem Scale (RSES) (39)	Increase
High instrumental coping skills	Kidcope (40)	Increase

Ethical Considerations:

Participants will be fully informed about the research study's ethical guidelines to ensure their rights and welfare are protected. Prior to data collection, participants will be asked to provide informed consent, ensuring they understand the purpose, procedures, risks, and benefits of participation. Furthermore, all research procedures will undergo review and approval by the Institutional Review Board to uphold ethical standards.

Risks and Benefits:

Participants will be informed about the potential risks involved in the study, such as discomfort or emotional unease when answering personal questions. However, participants will be assured that measures will be taken to minimize these risks, including the availability of support services if needed. While there may be no direct benefits to individual participants, they will be informed that their involvement could contribute valuable insights to benefit communities in humanitarian contexts, including Colombia, in the future.

Safety and Adverse Events:

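### The DSM-V primary outcome is analysed only as yes/no flags, so graded symptom change goes unused and the stated 80% power for d=0.5 does not hold for those flags

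*SAP*

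**What the plan says.** SAP section 2a asks about 19 symptoms over two weeks on a scale from 0 (never) to 4 (every day), where 2 means 3 to 6 days. Any one symptom in a domain is enough to trigger its flag; the rule begins: "A respondent will be flagged as requiring further inquiry for a given domain if they answer '2' or higher on at least one of the". The section concludes: "As such, this outcome will be operationalized as 12 dichotomous variables reflecting the 12 domains". Drug and alcohol use, self-harm and suicide items are asked as yes/no. The second primary outcome, RCADS-25, stays a summed score converted to a T-score.

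SAP section 5.1 fits OLS to the change in each outcome, with the baseline value added in Models 2 and 3. SAP section 7 compares change-score with endline models. Neither section introduces a DSM-V severity score.

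Protocol Table 1 labels the DSM-V construct as mental illness, with a hypothesised decrease. The null hypothesis under Statistical methods concerns levels of symptoms. The sample size paragraph gives its target as "To detect a medium effect size in our primary outcomes of interest", and sets that effect at d=0.5. The error rates are given as "assuming statistical power of 80% and a one-sided alpha of 0.05". The stated result is "we need a sample size of 63 adolescent girls in each study arm". It gives no flag rates and no calculation for a binary endpoint.

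**The concern.** The flag is a screening rule by the SAP's own description, and it discards most gradations of the scale. A girl going from 4 to 2 on an item stays flagged and contributes a change of zero. A girl going from 1 to 2 on a single item becomes a new flag. In a domain with two elevated symptoms, both must fall below 2 before any benefit registers. Neither the hypothesis (symptom levels) nor the effect size (a standardised mean difference) is what the flag measures.

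At stake is how a null result is read. In domains that RCADS-25 does not cover, such as somatic symptoms (somatization is a named target in the primary objective), a medium effect on symptom frequency could be missed while the protocol tells readers that power was 80%.

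**Working it through.** **Inputs from the protocol (sample size paragraph).** d=0.5; power 80%; one-sided alpha 0.05; 63 analysable girls per arm; "We expect approximately 20% attrition from baseline to T2"; and, for girls above threshold at baseline, "We expect this to result in the loss of an additional 10% of the initial sample".

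**Assumptions not in the documents.** Each domain has a normal latent severity, the intervention lowers it by 0.5 SD, and the control-arm flag rate p1 at T2 is varied.

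**Step 1: the plan's own figure.** n per arm = 2(z_alpha + z_beta)^2 / d^2.
- One-sided 0.05: 2(1.645 + 0.842)^2 / 0.25 = 49.5, so 50 per arm.
- Two-sided 0.05: 2(1.960 + 0.842)^2 / 0.25 = 62.8, so 63 per arm.

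The 63 matches a two-sided test, not the one-sided alpha written. Inflation reproduces: 63 / (1 - 0.20 - 0.10) = 90. Power for a continuous outcome at 63 per arm is Phi(0.5 x sqrt(63/2) - z_alpha), which is 87.7% one-sided and 80.1% two-sided. Both are carried forward because the protocol states one and its n implies the other.

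**Step 2: the same shift seen through the flag.** Treated flag rate p2 = Phi(Phi^-1(p1) - 0.5). Power = Phi((p1 - p2)/SE - z_alpha), with SE = sqrt([p1(1-p1) + p2(1-p2)]/63).

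Worked line for p1 = 0.20: p2 = 0.090, difference 0.110, SE 0.062, ratio 1.778. Power is Phi(1.778 - 1.645) = 55% one-sided and Phi(1.778 - 1.960) = 43% two-sided.

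| Control flag rate | Treated flag rate | Power, one-sided | Power, two-sided |
|---|---|---|---|
| 10% | 3.7% | 40% | 29% |
| 20% | 9.0% | 55% | 43% |
| 30% | 15.3% | 64% | 52% |
| 40% | 22.6% | 69% | 58% |
| 50% | 30.9% | 72% | 61% |
| 60% (maximum) | 40.3% | 73% | 62% |
| 80% | 63.4% | 68% | 56% |
| 90% | 78.3% | 57% | 45% |

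A pooled-variance formula gives values about one to two points lower (maximum 72% and 60%). If the baseline exclusion is not applied, n is 90 x 0.80 = 72 per arm and the maximum is 78% one-sided or 68% two-sided. It stays below 80% in every case.

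**Step 3: how much is due to the cut.** The 80% benchmark is for an ideal continuous score, and a single five-level item also falls short of that. In a simulation (4,000 runs per setting, cut points assumed 0.6 SD apart, 63 per arm, flag rates 20-80%), the 0-4 item had 72-85% power one-sided and 60-75% two-sided. The flag had 56-71% and 42-61%. Setting by setting, the cut itself costs roughly 12 to 19 percentage points.

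**The case against.** The strongest reply is that a threshold suits a trial about prevention. The protocol says it will exclude girls above threshold at baseline because nothing can be prevented in them. If that exclusion used these flags, the girl going from 4 to 2 would not be in the effect analysis. This stands in part: a flag is a coherent endpoint for prevention. But the exclusion is tied to a four-dimension measure that matches neither primary scale, and the SAP does not mention it, so whether it applies here is unclear. If it does, T2 flag rates would probably be low, where power is worst. The sample size would then need to rest on flag rates, and it does not.

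Other points that stand:
- RCADS-25 is also primary, stays continuous and loses nothing.
- Substance-use and suicide items are yes/no by design, so no gradation is lost there.
- The flag rates are assumed, and baseline adjustment in Models 2 and 3 could recover some power.
- The trial is a pilot that aims at preliminary effectiveness.

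A reader might infer that the trial as a whole cannot deliver its stated power. The documents do not support that, because the shortfall concerns the DSM-V flags only. A reader might also infer that the flags should give way to a 0-76 total of all 19 items. Nothing in the documents supports that total or a d of 0.5 on it. It would pool psychosis, mania, sleep and inattention with depression, and could dilute a domain-specific effect.

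**Conclusion.** The point holds for the DSM-V outcome in its scaled domains. The SAP collects graded responses and specifies no analysis that uses the grades, while the hypothesis is about symptom levels. The protocol's 80% power for d=0.5 in its primary outcomes is not true of the flags. It is about 40-72% one-sided or 29-61% two-sided for control flag rates of 10-50%, with a ceiling near 73% or 62%. The exact loss depends on flag rates that the documents do not give, but no flag rate reaches 80%.

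This rests on a normal latent severity, a 0.5 SD shift, 63 per arm, and a single unadjusted domain with no multiplicity correction. Not all of the gap can be recovered: a single 0-4 item would itself miss 80% in every simulated two-sided setting. It would be too strong to say that the flag ignores most of the benefit, or that a threshold is the wrong kind of endpoint for a prevention aim.

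**What to change.** - **SAP 2a and 5.1:** prespecify an analysis of the 0-4 DSM-V responses alongside the flags, for example the mean or sum of items within each scaled domain, at T2 and adjusted for the baseline value. A mean or sum is preferable to the highest item, which would again require every elevated symptom to fall before benefit shows.
- **SAP 2a and Protocol Table 1:** report the flags by arm as positive-screen proportions, not as mental illness. Keep the yes/no items as separate proportions.
- **Protocol, sample size paragraph:** limit the 80% statement to RCADS-25, and give power for the flags as a range under stated flag-rate assumptions and a stated sidedness.

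No new data are needed, since the item responses are already part of the questionnaire. The cost is one more analysis per scaled domain (ten, if substance use and suicide are the only two of the 12 built from yes/no items) and a less favourable stated power.
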